#### Threats to Confidentiality.

The Aim 2 study will gather personal information on all participants (name, email, address, etc.). This information will not be attached to any research study file. A unique ID number will be assigned to each participant, and all research documents pertaining to that participant (the data stored in REDCap or the transcriptions of the focus groups and individual interviews) will only be stored using that ID number. The file with baseline personal information and the file that links personal identifiers to ID numbers will be stored separately in the Emory encrypted computer in PI [name]'s office. Any later sharing of data from the study will be done according to an NIH-compliant data and resource sharing agreement, and those data will be completely de-identified.

#### **16. Potential Benefits to Participants**

Although we are careful not to assert this to potential study participants, we believe the program will provide them with knowledge and skills that will help them to better negotiate the additional dementia caregiving challenges they face during this time of Coronavirus pandemic – and in possible future crises.

In terms of a knowledge contribution to the field: If this trial demonstrates positive preliminary efficacy in reducing caregiver distress and enhancing caregiver mastery, it will add to the evidence that a psychoeducational approach (developing skills, knowledge, and competence through an active and interactive learning strategy) is effective with this important population. This study's approach is aligned with other work by the investigators and with investigators supported by the Emory Roybal Center for Dementia Caregiving Mastery and with clinical practice at the IMCC that developing caregiver competence reduces caregiver distress.

In terms of the caregiver knowledge that would be strengthened: the program aims to increase caregivers' knowledge about ways to manage day-to-day life with a person living with dementia, knowledge about infection control practices to minimize risk of viral infection; and knowledge about navigating the healthcare system.

As noted in #13, above, participants will receive a \$25.00 gift card (e.g., Visa card) for each research interview, focus group, and/or semi-structured interview in which they take part.

## **17. Data Analysis, Management and Confidentiality**

Quantitative data will be entered at the time of each Aim 2 interview directly into the dedicated project tablet computer and saved on Emory's secure REDCap platform. All data entry screens are set up in REDCap and, where possible, include data delimiters (i.e., skip patterns, valid range limits) to ensure correctness and minimize missing data. Data will be exported weekly and analyzed for data cleaning and verification. Upon completion of each cohort data-gathering point, all data will be merged for scale computation, aggregation, and analysis. We will use NVIVO 12 software to store and manage all qualitative data and to facilitate data analysis.

For quantitative analysis, we will test for group, time, and group-by-time effects for each of the outcomes (caregiver anxiety, depression, burden, stress, and mastery). In preliminary analyses, descriptive statistics and frequency distributions will be examined to identify outliers and ensure integrity of all data. For all multi-item scales, internal consistency will be examined using Cronbach's alpha and associated statistics (e.g., item-total correlations, alpha if item deleted). Preliminary analyses will examine baseline differences among completers and non-completers and by study arm (immediate/delayed) as a randomization check using 2-group comparison tests (t-tests and non-parametric equivalent tests for continuous variables (normally or non-normally distributed) and Chi-Square tests for categorical variables). The association of predisposing factors (demographics, Caregiving history, relationship and care recipient status at baseline) with changes in outcomes over time will be examined to identify significant covariates. Where significant associations with baseline measures are detected, these potential confounders will be controlled for in subsequent analyses using covariate model adjustments.

We will use repeated measures analysis to test 2 time by 2 group intervention (Immediate Participation in wave1 + immediate participation in wave 2) vs waitlist control (wave 1 + wave 2) change from baseline to post intervention at 8 weeks elapsed. Given final expected sample sizes of 45 subjects in each group (assuming 10% attrition), we will be powered at 80% with a 5% level of significance to detect moderate-to-large effect sizes for the group ( $f=0.297$ ), time ( $f=0.300$ ), and group-by-time ( $f=0.300$ ) effects. To examine intervention effects over time for the combined intervention groups (Immediate wave 1 (week 16-24) + Immediate wave 2 (week 24-32) + waitlist wave 1 participants after course participation (week 24-32)), we will use repeated measures mainly focused on pre-to-post intervention effects for the 3 groups combined, however a group effect will be tested to ensure that the WLC1 had no placebo carryover effect that altered their "baseline at 24 weeks" from the other 2 groups. Given the

sample sizes of 25 subjects in each of these 3 groups, we will be powered at 80% with a 5% level of significance to detect moderate-to-large effect sizes for the group ( $f=0.381$ ), time ( $f=0.381$ ), and group-by-time ( $f=0.381$ ) effects.

To address Aim 2 formative questions, Co-Investigator [name] will lead the team in a thematic analysis of the transcribed baseline focus group and post-intervention semi-structured interviews. We hope to pursue three lines of inquiry in this analysis that will be crucial for the next steps in our work: (1) In what ways might the overall concept of caregiver as healthcare navigator be sharpened? (2) In what ways might the delivery mechanism of the course be enhanced to improve caregiver learning (e.g., more interactivity)? (3) In what ways might individual components of the course be enhanced to improve caregiver learning (e.g., different formats; additional videos)? We expect that these analyses will provide compelling evidence for the feasibility, acceptability, and usability of the course.

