**Aim 2 [Weeks 16-52].** Drawing on the recruitment resources identified above, we will recruit 100 caregivers in two waves of 50 each to participate in a waitlist-control design pilot test. When 50 individuals are identified for the first wave, we will contact them, obtain their consent for participation, and, using established instruments delineated in Table 3 below to assess depression, anxiety, burden, and mastery, gather, through 30-minute phone or video interviews, baseline quantitative data on mood and caregiving competency. Once all participants in each wave have completed their baseline quantitative interviews, we will randomly assign half (25) to immediately enroll in and begin the course; we will inform the other half of the group (25) that the course will be open for their enrollment after a waiting period of approximately eight weeks, the time it will take the immediate participants to complete the course. All participants will again be interviewed at that 8-week point, following the immediate group's course completion and prior to the wait-list group's enrollment. All will be interviewed again 8 weeks later. This same pattern of data collection and random assignment will be followed with the second wave participants.

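### The main 8-week comparison does not prespecify adjustment for each outcome's own baseline score or for randomisation wave; a significance screen that names neither decides what enters the model.

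*Combined protocol and SAP*

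**What the plan says.** Section 17 (Data Analysis, Management and Confidentiality) defines the main comparison: "We will use repeated measures analysis to test 2 time by 2 group intervention". The quantity compared is "change from baseline to post intervention at 8 weeks elapsed", and the two waves are pooled: "Immediate Participation in wave1 + immediate participation in wave 2) vs waitlist control (wave 1 + wave 2". No covariate and no wave term is named. The sample size statement reads "Given final expected sample sizes of 45 subjects in each group (assuming 10% attrition"), and "we will be powered at 80% with a 5% level of significance", with a detectable group-by-time effect of f=0.300.

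Covariates are covered earlier in the same section. The plan will examine "The association of predisposing factors (demographics, Caregiving history, relationship and care recipient status at baseline) with changes in outcomes over time". It then adds: "Where significant associations with baseline measures are detected, these potential confounders will be controlled for in subsequent analyses using covariate model adjustments". No significance threshold is given. The outcome's own baseline score and wave are not among the listed factors.

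Section 6 (Procedures Involved, Aim 2) sets the order of events: "Once all participants in each wave have completed their baseline quantitative interviews, we will randomly assign half (25") to start the course at once. The second wave of 50 follows the same pattern. Every outcome is therefore measured before allocation, and allocation is 25:25 within each wave.

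**The concern.** The baseline score enters the planned model only as the first level of time. That gives a comparison of change scores, not adjustment for baseline. Under randomisation, adjusting the 8-week score for its own baseline never has a larger error variance and usually has a smaller one. The trial is powered only for moderate-to-large effects and already collects the baseline score on everyone, so the precision costs nothing.

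The text also does not settle which model will be fitted. The list of factors to be screened excludes the baseline score, but the next sentence speaks of baseline measures, which could include it. Two analysts following Section 17 could report different main results for the same outcome. Wave is not named on any reading, although it is the unit within which caregivers are randomised.

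**Working it through.** **Inputs.** From Section 17: 45 analysed per arm (50 × 0.9), 90 in total; 5% significance; 80% power; f=0.300 for group-by-time. From Section 6: 25:25 allocation in each of two waves. Assumed, because the documents do not give them: the baseline-to-8-week correlation ρ (0.4 to 0.9), equal variances at the two times, and the difference between waves in mean change.

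**1. The plan's own figure.** In a 2 × 2 design the group-by-time F test, on 1 and 88 degrees of freedom, is the square of the t-test on change scores. For 80% power the noncentrality must be λ = 8.02. Then f = √(8.02/90) = 0.299, which is an effect of 2 × 0.299 = 0.60 SD of change. The stated f=0.300 gives 80.4% power. The plan's figure therefore reproduces, and it is the figure for the unadjusted test.

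**2. Adjusting for the baseline score.** With outcome variance σ², the change score has variance 2(1−ρ)σ², and the 8-week score adjusted for baseline has residual variance (1−ρ²)σ². The ratio is

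(1−ρ²) / [2(1−ρ)] = (1+ρ)/2, which is never above 1.

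For the same true effect, the adjusted test has λ = 8.02 / [(1+ρ)/2] on 1 and 86 degrees of freedom (baseline and wave both fitted). At ρ=0.5, for example, 8.02/0.75 = 10.7 and power is 90%. The equivalent unadjusted sample is 45 / [(1+ρ)/2] per arm.

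| ρ | (1+ρ)/2 | Power, change score | Power, baseline-adjusted | Equivalent n per arm, unadjusted |
|---|---|---|---|---|
| 0.4 | 0.70 | 80% | 92% | 64 |
| 0.5 | 0.75 | 80% | 90% | 60 |
| 0.6 | 0.80 | 80% | 88% | 56 |
| 0.7 | 0.85 | 80% | 86% | 53 |
| 0.8 | 0.90 | 80% | 84% | 50 |
| 0.9 | 0.95 | 80% | 82% | 47 |

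The formula ignores the small cost of chance baseline imbalance. Simulated powers are lower by about 1 point at most.

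**3. If the screen is read to include the baseline score.** Baseline correlates with change at −√((1−ρ)/2), which runs from −0.55 at ρ=0.4 to −0.22 at ρ=0.9. In 20,000 simulated trials per value of ρ, the baseline score passed a 5% screen in about 100%, 100%, 99%, 96%, 83% and 54% of trials for ρ = 0.4 to 0.9. Screening and then adjusting gave power within 1 point of always adjusting: 82.4% against 82.9% at ρ=0.8, and 80.6% against 81.3% at ρ=0.9. On this reading the power loss is close to nil.

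**4. Omitting wave.** Differences in level between waves cancel in change scores, so only a difference in mean change matters. If mean change differs by w SD of change and the waves are balanced across arms, the residual variance is inflated by 1 + w²/4. The critical value is then in effect multiplied by √(1 + w²/4).

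- w = 0.5: multiplier 1.03, power 78% instead of 80%, type I error about 4.3%.
- w = 1: multiplier 1.12, power 73%, type I error 2.9%. This is extreme, since it exceeds the 0.60 SD effect the trial is powered for.

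Simulation with random 10% attrition gave 77.9% and 72.0% power, and type I error of 4.5% and 2.8%.

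**5. Leaving the choice open.** If the better of the change-score and baseline-adjusted results were reported, type I error would be 6.3% (ρ=0.8) to 7.8% (ρ=0.3) in simulation. This is a ceiling on what the ambiguity permits, not a prediction.

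**The case against.** The strongest reply is that the plan contains no error. It names a valid model, a contrast and a sample size that match one another, and randomisation protects the change-score test from bias. That stands, and it is why this is a point about efficiency and prespecification only.

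Second, a natural reading of baseline measures covers the instrument scores, since Section 6 calls the baseline interview results baseline data. On that reading almost no power is lost (step 3). This also stands, but the sentence before it lists the factors to be screened and omits those scores. The ambiguity remains, and one sentence would remove it.

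Third, the size depends on an assumed correlation and on fixing the effect in SD of change. If the raw effect is held at 0.5 SD instead, change-score against adjusted power is 86% against 91% at ρ=0.7, 96% against 97% at 0.8, and over 99% for both at 0.9. The gain may therefore be small when the correlation is high. It is never a material loss.

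Fourth, the wave effect is minor and conservative. Agreed: wave is worth including mainly so that the analysis matches the randomisation.

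Finally, this is a pilot, and the documents name no primary outcome. Section 17 nevertheless makes a formal 80% power, 5% significance claim for this comparison, and Section 2 seeks preliminary efficacy, so the model behind it should be fixed in advance.

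**Conclusion.** The concern holds. As written, the main 8-week analysis is an unadjusted change-score test with the waves pooled, and the text does not settle whether the baseline score will be adjusted for. If it is left out, power is 80% where 82% to 92% was available from the same 45 per arm, for assumed correlations of 0.9 down to 0.4. If the screen admits it, the loss is within 1 point, and what remains is an unclear specification. Omitting wave costs about 2 points of power if mean change differs between waves by 0.5 SD of change, and nothing if it does not differ. None of this biases the estimate. The change should be made, but the trial does not fail without it.

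A related caution: Section 17 also tests a group main effect for each outcome. That effect averages the baseline and 8-week scores and so carries only half of the course effect. The plan does not say it will be read as a test of the course, and it should not be.

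**What to change.** In Section 17, state for each outcome that:

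- the efficacy result is the difference between arms at the 8-week interview, from a linear model (or a mixed model with a common baseline mean in both arms);
- that outcome's baseline score and wave are fixed covariates, included whatever any screen shows;
- the conclusion about efficacy rests on this contrast and not on the group or time main effects;
- models with covariates chosen by screening are sensitivity analyses.

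The cost is a few sentences and two model degrees of freedom. No new data are needed, and the existing sample size statement can stand as a conservative one.

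### The pooled pre-to-post analysis has no untreated comparator, so its change should be labelled descriptive; waitlist wave 2 is left out without a stated reason, and a non-significant group test cannot show that waitlist wave 1 is unaltered.

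*Combined protocol and SAP*

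**What the plan says.** Section 17 first compares the immediate and waitlist groups, both waves combined, on "change from baseline to post intervention at 8 weeks elapsed". It expects 45 per group after 10% attrition.

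It then adds a second analysis: "To examine intervention effects over time for the combined intervention groups". These groups are immediate wave 1 (weeks 16-24), immediate wave 2 (weeks 24-32) and waitlist wave 1 once it takes the course (weeks 24-32), with 25 in each. For them, "we will use repeated measures mainly focused on pre-to-post intervention effects for the 3 groups combined". As a safeguard, "a group effect will be tested to ensure that the WLC1 had no placebo carryover effect" that would have changed its week-24 starting value relative to the other two groups. The plan gives no margin, no confidence-interval criterion and no action if the test is significant.

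Section 6 (Aim 2) gives every participant the same interviews: "All participants will again be interviewed at that 8-week point", then "All will be interviewed again 8 weeks later". It applies this schedule to the second wave too. Covariate adjustment depends on a screen: "Where significant associations with baseline measures are detected, these potential confounders will be controlled for in subsequent analyses".

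**The concern.** Every group in the second analysis is treated during the interval analysed. The time effect is therefore the course effect plus whatever else moves scores over those weeks: change in pandemic conditions, regression to the mean, repeated interviewing. The group-by-time term compares treated groups with one another, so it cannot isolate the course effect either. Yet the plan describes the result as an intervention effect and gives it its own power statement beside the controlled comparison.

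Two further points follow. On the Section 6 schedule, waitlist wave 2 also has a pre-course interview (8 weeks) and a post-course interview (16 weeks), but it is missing from the pool and no reason is given. And absence of significance in a test on 25 per group is not evidence that waitlist wave 1 started the course unaltered.

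**Working it through.** **Inputs.** From Section 17: 3 groups of 25 (75 in all); 45 v 45 in the randomised comparison; 10% attrition; 5% level; 80% power. Assumed, because the plan gives none of them: size and direction of drift, pre-post correlation ρ of 0.5 or 0.7, a true effect of 0.3 SD, a shift of 0.5 SD in waitlist wave 1. All are in units of the outcome SD; tests are taken as two-sided.

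**The plan's own figures.** One-way noncentral F with noncentrality N·f²: 2 × 45 gives f = 0.2986 at 80% power, which reproduces the stated 0.297 to 0.300. 3 × 25 gives f = 0.366 for the group effect, not the stated 0.381; 0.381 fits about 23 per group (0.382). The stated figure is thus slightly conservative, and nothing below depends on it.

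**Drift in the pooled test.** The SD of change is √(2(1−ρ)): 1.000 at ρ = 0.5 and 0.775 at ρ = 0.7. The noncentrality is net change ÷ SD of change × √N.

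| True effect, drift | N | ρ = 0.5 | ρ = 0.7 |
|---|---|---|---|
| None, 0.2 SD improving | 75 | 1.73 → 40% | 2.24 → 60% |
| None, 0.2 SD improving | 68 (75 less 10%) | 1.65 → 37% | 2.13 → 55.5% |
| None, 0.2 SD improving | 100 (waitlist wave 2 added) | 2.00 → 51% | 2.58 → 72% |
| 0.3 SD benefit, 0.2 SD worsening | 75 | 0.87 → 13% | 1.12 → 20% |

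Each percentage is the share of trials with a significant result in favour of the course. With a 0.3 SD benefit and no drift the shares would be 73% and 91% at N = 75. Drift can therefore create a benefit or hide one, and adding waitlist wave 2 does not cure this.

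**The group test.** With one group of three shifted, f = shift × √2/3. A 0.5 SD shift gives f = 0.236 and noncentrality 75 × 0.236² = 4.17; the 2-df test on pre-course values has 42% power. Read instead as waitlist wave 1 against the other two (25 v 50), the noncentrality is 0.25 ÷ (1/25 + 1/50) = 4.17 on 1 df, and power is 52%. For 80% power the shift must be about 0.78 SD or 0.70 SD respectively. The plan's own f = 0.381 corresponds to 0.381 ÷ 0.471 = 0.81 SD. A repeated-measures group main effect would also average pre and post, and so would not isolate the starting value at all.

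**The randomised comparison, 45 v 45, effect 0.3 SD.** Drift common to both arms cancels.

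- Change scores: SE = √(2(1−ρ) × 2/45) = 0.211 (ρ = 0.5) or 0.163 (ρ = 0.7); power 29% or 44%.
- Baseline-adjusted: SE = √((1−ρ²) × 2/45) = 0.183 or 0.151; power 37% or 50%.

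**The calendar.**

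| Place | What it implies |
|---|---|
| Section 17 | Immediate wave 1 takes the course in weeks 16-24; by the same offsets waitlist wave 2 would take it in weeks 32-40 |
| Section 6, Aim 1 and Table 1 | Aim 1 runs to week 24; course finalised about weeks 20-24; Aim 2 recruitment begins about week 24 |
| Section 6, Aim 2 | First-wave baseline about week 22; data to about week 48; last interview at 16 weeks |
| Section 1 | 24 weeks per participant |
| Section 9 | Aim 2 enrolment in months 4-9, participation about 5 months, project one year |
| Section 13 (payments) | Interviews at 3 and 5 months |

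A participant enrolled in month 9 with a last interview at 5 months finishes in month 14. If wave 1 started the course at week 28 (an assumption) with the same 8-week offsets, waitlist wave 2 would take it in weeks 44-52, at the edge of the project.

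**The case against.** The strongest reply is that this is a pilot with an intact randomised comparison. Section 17 lists that comparison first and powers it, and Section 2 ties preliminary efficacy to the waitlist-control test. That stands. A reader might infer that the trial's efficacy claim rests on uncontrolled data; the documents do not support this, because the pooled result is never called efficacy. What remains at fault is the intervention-effect label.

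A reader might also infer that waitlist wave 2 was dropped arbitrarily. The documents do not show that either: the calendar conflicts make timing a plausible reason, though none is stated.

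Nor do they support a claim about which way drift will bias the result. Section 3 reports rising strain in a waitlist group, but that is one outcome over six months in a different trial.

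Finally, the plan does disclose that only moderate-to-large effects are detectable, and the 25 v 50 reading of the group test is kinder to it than the 2-df reading. Both readings still miss a 0.5 SD shift in about half of trials or more. Change from baseline is valid under randomisation, so baseline adjustment is a gain in precision and not a correction of bias.

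**Conclusion.** The point holds, confined to the second analysis and its label. The pooled pre-to-post change mixes course effect with drift. Under an assumed improving drift of 0.2 SD and no course effect, it would show benefit in 40% to 60% of trials at N = 75, or 37% to 55% at N = 68. An assumed worsening drift would mask a real benefit instead. The group test has 42% to 52% power against a 0.5 SD shift, so non-significance gives little reassurance. The omission of waitlist wave 2 is unexplained, and the timetable is inconsistent enough that its post-course interview may not fit. The drift sizes, drift direction, correlations and shift are assumptions; the absence of an untreated comparator does not depend on them. The randomised 8-week comparison is unaffected. Severity: low; the change should be made, but the trial's main comparison does not hang on it.

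**What to change.** 1. State that any efficacy conclusion comes from the randomised 8-week comparison, with prespecified adjustment for the baseline value of the outcome in place of adjustment only after a significance screen.
2. Label the pooled pre-to-post change descriptive. Report the waitlist's untreated 8-week change with its 95% CI beside it. Include waitlist wave 2 (8-week to 16-week interviews) if its post-course interview falls within the project; otherwise say why it is left out.
3. Replace the group test with the pre-course difference between waitlist and immediate groups and its 95% CI (half-width about 0.40 SD at 50 v 50, 0.42 SD at 45 v 45). State that this does not separate carryover from drift.
4. Reconcile the timetable across Section 1, Section 6 (Aim 1, Table 1 and Aim 2), Section 9, Section 13 (payments) and Section 17.

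The cost is some analysis wording, and no interviews beyond those in Section 6 once the calendar is settled. The downside is that the pooled figure can no longer be presented as an intervention effect. Adding waitlist wave 2 narrows the interval around a figure that still contains drift, so the descriptive label is needed either way.

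### The second power statement gives f = 0.381 for both a 1-df and a 2-df effect, which cannot both be the 80%-power value, and 0.381 does not follow from the printed 25 per group

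*Combined protocol and SAP*

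**What the plan says.** Section 17 (Data Analysis, Management and Confidentiality) contains two power statements.

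- **First statement, immediate versus waitlist, two groups by two times.** It rests on "final expected sample sizes of 45 subjects in each group (assuming 10% attrition") and gives detectable f of 0.297 for group and 0.300 for time and for group-by-time, at 80% power and a 5% level.
- **Second statement, pooled course-takers.** The groups are "Immediate wave 1 (week 16-24) + Immediate wave 2 (week 24-32) + waitlist wave 1 participants after course participation (week 24-32"). The analysis is "mainly focused on pre-to-post intervention effects for the 3 groups combined", with a group effect tested as a check on the waitlist group's starting point. The basis is "sample sizes of 25 subjects in each of these 3 groups, we will be powered at 80% with a 5% level of significance", "for the group ( $f=0.381$ ), time ( $f=0.381$ ), and group-by-time ( $f=0.381$ ) effects". No attrition is mentioned here.

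Section 6 (Procedures Involved, Aim 2) shows that 25 is the number randomised to each arm in each wave, before any loss. Neither statement gives a within-subject correlation or a noncentrality convention.

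**The concern.** Two features of the second statement do not fit its own design.

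First, the effects have different degrees of freedom. Two time points give time 1 df. Three groups give group and group-by-time 2 df each. Equal values for group and group-by-time are therefore unremarkable, but equal values for time and group-by-time are not.

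Second, the first statement takes off attrition and says so. The second prints the full randomised number and does not say whether attrition was considered.

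What is at stake is limited but real. The pooled analysis is aimed mainly at the pre-to-post change, which is the time effect, and that is the figure that fits worst. As printed, a reader cannot tell which n, correlation or convention produced 0.381.

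**Working it through.** **Inputs.** From Section 17: alpha 0.05, power 0.80; first statement 2 groups, N = 2 × 45 = 90; second statement 3 groups, N = 3 × 25 = 75, two time points, f = 0.381 for every effect. From Section 6: 25 randomised per arm per wave. The within-subject correlation (rho) is not given, so a range is tried.

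**Method.** Noncentral F. Power = P(F′ > Fcrit), where F′ has d1 and N − k df (k groups) and noncentrality λ. Convention A sets λ = N f², so detectable f = √(λ/N), with λ the value that gives 80% power.

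**Step 1. Check against the first statement.** N = 90, df (1, 88): the required λ is 8.02, so f = √(8.02/90) = 0.299. Power is 79.6% at f = 0.297 and 80.4% at f = 0.300. Convention A therefore comes within half a power point of both printed values.

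**Step 2. Apply it to the second statement.** At N = 75 the required λ is 8.06 for 1 df and 10.05 for 2 df, on 72 error df:

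- time: √(8.06/75) = 0.328
- group and group-by-time: √(10.05/75) = 0.366

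At f = 0.381, λ = 75 × 0.381² = 10.89, which gives 90.2% power for time and 83.3% for the 2-df effects.

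**Step 3. Vary the analysed n.** 25 less 10% is 25 × 0.9 = 22.5.

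| n per group | N | f at 80%, time (1 df) | f at 80%, 2-df effects | Power at 0.381, time | Power at 0.381, 2-df |
|---|---|---|---|---|---|
| 25 | 75 | 0.328 | 0.366 | 90.2% | 83.3% |
| 24 | 72 | 0.335 | 0.374 | 89.0% | 81.6% |
| 23 | 69 | 0.342 | 0.382 | 87.7% | 79.7% |
| 22 | 66 | 0.350 | 0.391 | 86.2% | 77.7% |

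The 2-df effects match 0.381 at about 23 per group. The time effect reaches 0.381 only at about N = 56, or 19 per group, a number the plan nowhere uses. No row gives 0.381 in both columns.

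**Step 4. Does a correlation-based convention rescue it?** Convention B (an assumption, since no correlation is given) sets λ = N f² × 2/(1 − rho) for within-subject effects. At N = 75:

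| rho | Time | Group-by-time | Ratio |
|---|---|---|---|
| 0 | 0.232 | 0.259 | 1.116 |
| 0.5 | 0.164 | 0.183 | 1.116 |
| 0.7 | 0.127 | 0.142 | 1.116 |
| 0.9 | 0.073 | 0.082 | 1.116 |

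The correlation multiplies both effects equally, so it cancels from the ratio: √(10.05/8.06) = 1.116. None of these values reaches 0.381. For the group effect, the matching form λ = N f² × 2/(1 + rho) gives 0.259 at rho 0 and 0.357 at rho 0.9, still short of 0.381. Convention B also misses the first statement's time and group-by-time values (N = 90: 0.211 at rho 0, 0.149 at rho 0.5, against 0.300 printed), so Convention A is used for the replacement values.

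**The case against.** **The assurance is not false.** At 25 per group, power at f = 0.381 is at least 80% for all three effects, so 0.381 is a safe common bound. That is correct, and it means the statement does not promise power the study lacks at that n. But the plan says "we will be powered at 80% with a 5% level of significance" without an *at least*, and the first statement's values sit within half a point of exactly 80%. Read in the same way, the second statement misses by about 10 points for time.

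**The convention is inferred.** Convention A gives 0.299 for all three 1-df effects, whereas the plan prints 0.297 and 0.300, so the authors' exact method is not identified. This makes the n mismatch conditional on the convention, although no convention tried gives 0.381 at 25 per group. It does not touch the df point, which holds under either convention and at every correlation tried.

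**The attrition explanation is conjecture.** Rounding 22.5 up to 23 fits and rounding down to 22 does not. At 24 per group, which is not a 10% loss, the 2-df power is 81.6%, also not far off. The printed 25 can simply be read as the number before attrition. What stands is narrower: the second statement does not say how it treats the attrition that the first allows for.

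**The 10% may not carry over.** It is attached to the 8-week comparison. Wave 1 waitlist participants reach their post-course interview about 16 weeks after baseline, so their losses could differ. This affects the second decimal of the replacement values, not the finding.

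**Conclusion.** The concern holds, as a minor arithmetic error with high confidence. The detectable f for the 2-df effects is about 1.12 times that for time, so 0.381 cannot be the 80%-power value for both. This rests only on two time points, three groups and a shared error term.

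The mismatch with 25 per group is smaller for the 2-df effects (0.366 against 0.381) than for time (0.328 against 0.381), and its exact size rests on Convention A. That 0.381 came from a 2-df calculation at about 23 per group is a plausible inference, not something the document states.

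At the printed n the error understates the study's sensitivity. It leaves the sample size and the immediate-versus-waitlist comparison unaffected.

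**What to change.** Rewrite the one sentence in Section 17:

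- State the analysed n per group and whether attrition has been taken off. With the first comparison's 10%, this is 22-23 per group. If a different loss is expected for the wave 1 waitlist group, say so.
- Give separate detectable values. On the first statement's apparent convention these are about f = 0.34-0.35 for time (0.342 at 23 per group, 0.350 at 22) and 0.38-0.39 for group and group-by-time (0.382 and 0.391).
- Name the noncentrality convention and the within-subject correlation assumed. If the authors used another convention, their own recalculated values should replace these.

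The cost is one sentence. The design, sample size, pooled groups and analysis stay as they are.
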